6.4.3 Viral sequencing

Individuals with new seroconversion to HIV will have sample sent for viral sequencing and phylogenetic analysis. Individuals with detectable HCV RNA after completion of HCV treatment or new infection during the follow up period will have current sample, and baseline stored sample sent for viral sequencing and phylogenetic analysis.

6.4.4 Linkage to care

Any participant who seroconverts to HIV+ will be immediately linked to care, in DC or in Baltimore.

6.5 Early Termination Visit

Participants who discontinue HCV treatment prior to treatment completion for medical or personal reasons will be given the option of being followed as per study schedule for lab monitoring.

7 Potential Risks and Benefits

7.1 Potential Risks

Given this investigation is centered on a standard model of care, the main risks are related to any blood draw outside of standard of care, and loss of confidential data.

Participants who receive treatment for HCV may experience side effects from the medication they receive. They will receive one of the following medication to treat hepatitis C: Elbasvir/Grazoprevir (Zepatier), Sofosbuvir/Ledipasvir (Harvoni), Sofosbuvir/Velpatasvir (Epclusa), Glecaprevir/Pibrentasvir (Mavyret), Sofosbuvir/Velpatasvir/Voxilaprevir (Vosevi).

Common side effects (those that occurred in more than 5% of the patients in clinical trials) each medication is listed below:

Elbasvir/Grazoprevir (Zepatier):

- Fatigue
Headache

Sofosbuvir/Ledipasvir (Harvoni):

- Fatigue

- Headache
- Nausea
- Diarrhea
- Insomnia

Sofosbuvir/Velpatasvir (Epclusa):

- Headache
- Fatigue
- Nausea
- Insomnia
- Lack of energy

Glecaprevir/Pibrentasvir (Mavyret):

- Headache
- Fatigue
- Nausea
- Diarrhea

Sofosbuvir/Velpatasvir/Voxilaprevir (Vosevi):

- Headache
- Fatigue
- Diarrhea
- Nausea
- Insomnia
- Lack of energy

Other potential risks include risks of phlebotomy that include: pain, bruising, fainting and very rarely, infection. These risks will be minimized by having trained staff perform the procedure.

There is potential for loss of confidentiality, which will be minimized by providing privacy during study visits. In addition, all laboratory specimens, and research records will be coded by a number to maintain subject confidentiality. Electronic data will be password protected.

Potential risks from MRI are outlined in Appendix C. Of note, the cardiac MRI is considered to be greater than minimal risk. If you elect to have the cardiac MRI, you will be required to sign a separate consent form which will explain the procedure and risks in more detail.

7.2 Potential Benefits

Subjects may be cured of hepatitis C during the course of this study. Also, they will contribute to the body of scientific research on treatment of hepatitis C and cardiovascular risk in people with living with HIV and/or HCV. Furthermore, by achieving functional cure of HCV, subjects will no longer be a potential source of HCV transmission in the community. It is possible that subjects will receive no benefit from the study participation.

8 Stored Samples and Future Research

We will study the viral and host immunity to HCV and HIV in all patients. The results will be used to characterize each individual with regards to immune status and chronicity of disease. Studies on research samples may include the following:

- A] HCV genome sequencing may be performed on plasma using the protocol as described and compared for variability and relatedness of sequences.
- B] We will screen sera from all patients for differential expression of protein using multiplex cytokine arrays, which has the capability of detecting several different cytokines and other biologically relevant proteins.
- C] We will perform detailed phenotypic and functional evaluation of immune cell types in the periphery. This will help us in determining the nature of antiviral immune responses in patients who are chronically infected, achieve SVR and acquire new HCV and HIV infections. Determination of specific immune defects in these individuals are important milestones in deciding future therapeutics and protective immunity to reinfection. Exhaustion and activation markers on T, B and NK cells will be quantified. Specific immune responses against pooled HCV peptides will be performed using an ELISPOT assay and/or flow cytometry.

Future use of the specimens will be based on the scientific merit of the investigation and would be decided by the Principal Investigator. They would be related to the study of HCV and/or HIV. Other investigators may wish to study these samples and/or data. In that case, IRB approval must be sought prior to any sharing of samples and/or data. Any clinical information shared about the sample would similarly require prior IRB approval. If approved, and once a Material Transfer Agreement (MTA) has been established, the study team may send de-identified samples to the collaborators. Investigators will use stored samples only for research.

8.1 Intended Use:

Some blood samples may be stored for future analysis in this research study. These samples will be stored by the IHV researchers and may be used in future research to learn more about HCV and HIV, the immune system and/or other related medical conditions. The blood will be used over time to gain a better understanding of the pathogenesis of HCV and HIV. Genetic testing will be performed. Different analytical

and laboratory methods will be employed including but not limited to: PCR, ELISA, ELISPOT and immunohistochemistry; RNA/DNA, cytokine and antibody quantitation; viral particle detection and identification of genetic markers. The consent will include language for specimen storage.

8.2 Storage:

Samples will be kept in secure facilities with limited access. Samples and data will be stored using a unique identifier. Only investigators and study staff will have access to the samples and data.

8.3 Tracking:

Extra blood samples will be stored using a unique identifier that only the study team can trace back to the participants. These stored samples as well as a linkage file will be maintained in a database that will be managed by the Investigators and/or Study Coordinators and will be maintained on the IHV server. This database will also be stored on the password-protected computer of the Lead-Investigator/Study Coordinator in an encrypted and/or password-coded file.

8.4 Disposition at the Completion of the Protocol:

At the completion of the protocol (termination), samples and data will either be destroyed, or after IRB approval, transferred to another existing protocol. Final disposition of any samples cannot be done without written permission from the PI.

8.5 Reporting the Loss or Destruction of Samples/Specimens/Data to the IRB:

- Any loss or unanticipated destruction of samples or data resulting in a violation that compromises the scientific integrity of the data collected for the study will be reported to the IRB.
- Participants may request at any point not to have their samples stored. In this case, the Principal Investigator will destroy all known remaining samples and report what was done with the samples to both the participant and to the IRB. This decision will not affect the subject's participation in any other protocols.

Generally, the results from the research stored samples will not be given to the participant's primary care provider or appear in the medical record. This is because the test results, unlike routine medical testing, may be experimental or preliminary. The relevance of these tests to direct patient care may be unknown. At the participant's request, the results of any research tests will be discussed with the primary care physician by the Investigators.

9 Assessment of Safety

As this is a pilot, non-randomized, controlled perspective study involving standard of care treatment, with interventions limited to non-standard of care blooddraws and cardiac imaging, safety issues are not expected. Only those reportable Adverse Events (AEs) related to the research procedures will be reported or those not expected from cardiac MRI (expected MRI AEs are Mild allergic reaction to contrast agents; Acute renal insufficiency related to iodine-based contrast agent; Subcutaneous injection of contrast agents). The PI will review the safety data and report any unexpected events to the IRB along with the annual continuing review.

9.1 Recording/Documentation

At each contact with the patient, information regarding adverse or unexpected events related to research procedures will be elicited by appropriate questioning and examinations and will be immediately recorded in electronic progress notes. Source documents will include an electronic health record and laboratory reports. Source documents will be reviewed in a timely manner by the research team.

9.2 Definitions

Adverse Event: Any untoward medical occurrence in a human subject, including any abnormal sign, symptom, or disease, temporally associated with the subject's participation in research, whether or not considered related to the subject's participation in the research.

Protocol Deviation: Any change, divergence, or departure from the IRB approved study procedures in a research protocol. Protocol deviations are designated as serious or non-serious and further characterized as:

- Those that occur because a member of the research team deviates from the protocol.
- Those that are identified before they occur, but cannot be prevented.
- Those that are discovered after they occur.

9.3 Reporting Protocol deviations, AEs and Deaths

Anticipated deviations in the conduct of the protocol will not be reported to the IRB unless they occur at a rate greater than anticipated by the study team. Expected adverse events will not be reported to the IRB unless they occur at a rate greater than that known to occur in those having phlebotomy procedures normally. If the rate of these events exceeds the rate expected by the study team, the events will be classified and reported. Deaths related to the natural history of hepatitis will be reported at the time of continuing review (see annual reporting to the IRB). If a death occurs while the participant is at the NIH it would be reported to the Clinical Director of the Clinical Center, the Clinical Director of NHLBI, and the UMB PI in real time as reported as required by UMB IRB.

9.3.1 Expedited Reporting to the IRB

Any reportable new information (RNI) will be reported to the IRB within 5 business days. This includes:

- 1) Information that indicates a new or increased risk, or a safety issue.
- 2) Any harm experienced by a subject or other individual, which in the opinion of the investigator are unexpected and probably related to the research procedures.
- 3) Non-compliance with the federal regulations governing human research or with the requirements or determinations of the IRB, or an allegation of such non-compliance.
- 4) Failure to follow the procedure due to the action or inaction of the investigator or research staff.
- 5) Breach of confidentiality.
- 6) Change to the protocol taken without prior IRB review to eliminate an apparently immediate hazard to a subject.
- 7) Complaint of a subject that cannot be resolved by the research team.
- 8) Premature suspension or termination of the research by the sponsor or the investigator.
- 9) Audit, inspection, or inquiry by a federal agency.
- 10) Written reports of study monitors.

The NIH site PI and/or study team will report any RNI to the UMB PI so that they are reported within the above timeframe to the UMB IRB.

9.3.2 Waiver of Reporting Anticipated Protocol Deviations, Expected non-UP AEs and Deaths

Deviations in the protocol that do not rise to the level of serious or continuing non-compliance, and unanticipated or adverse events that are NOT serious, unexpected AND related to research protocols need not be reported in an expedited manner to the IRB. Rather, such RNI should be reported as a group at the time of annual renewal (see below)

9.4 Annual Reporting to the IRB

The following items will be reported to the University of Maryland IRB in summary at the time of Continuing Review:

- Serious adverse events or deaths that are not related to the research
- All adverse events associated with research including expected AEs Protocol deviations. This includes AEs related to phlebotomy within 48 hours of procedure.
- Serious, continuing, and minor non-compliance
- Any trends or events which in the opinion of the investigator should be reported

9.4.1 Type and Duration of the Follow-up of Subject after Adverse Events

All SAEs and non-serious AEs identified in this study will be followed until resolution or until the PI judges the AE/SAE has stabilized and no more follow-up is required. This requirement indicates that the follow-up may be required for some events after the participant discontinues participation from the study. These events will be reported to the IRB annually.

10 Withdrawal of a Subject

A participant may withdraw from the study at any time. As part of their duties to ensure that research participants are protected, the IRB, IHV, or other government agencies may discontinue the study at any time. Voluntary withdrawal from the protocol may occur at any time at the request of either the participant or the PI. If a request is made to withdraw from the protocol, all further planned study procedures will be immediately cancelled and further follow-up will be terminated. Samples and data already collected may continue to be used. If a patient becomes pregnant during the course of the study, the patient will be discontinued from the study.

Of note, women who become pregnant during the study will be withdrawn and hepatitis C treatment will be stopped. She will be instructed to see an obstetrician and inform the doctor of her specific hepatitis C regimen at the time of conception. If the partner of a man on hepatitis C treatment gets pregnant, he will not be withdrawn from the study, but told to use condoms during intercourse and instruct his partner to let her obstetrician know of his hepatitis C treatment regimen at the time of conception.

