4.2 Subject Inclusion Criteria

To be eligible for participation on this protocol, a participant must satisfy all of the following conditions:

1. Age ≥ 18 years old
2. Able and willing to sign informed consent

3. Chronically infected with HCV (any genotype), defined as any individual with documentation of positive HCV antibody and positive HCV RNA test (HCV RNA of 2,000 IU/mL or greater)
4. If HIV+, suppressed on a stable, protocol-approved, ARV regimen for \geq 8 weeks prior to enrolling in the study
 - a. HIV RNA $<$ 50 copies/mL (or $<$ LLOQ if the local laboratory assay's LLOQ is \geq 50 copies/mL) prior to Screening. Subjects with an isolated or unconfirmed HIV RNA $>$ 50 copies/mL (or $>$ LLOQ if the local laboratory assay's LLOQ is \geq 50 copies/mL) are not excluded.
 - b. CD4 count $>$ 100 cells/mm³
5. Willing to have samples stored for future use
6. If tested positive for NS5A resistance-associated polymorphisms or PEG-IFN and ribavirin experienced, able to tolerate ribavirin-containing regimen for 16 weeks. Ribavirin will be administered at the discretion of the PI.
7. Women of childbearing potential who receive ribavirin will have to be willing to commit to abstinence from sexual activity, or use of two forms of contraceptive during treatment and for the 6 months after completion of ribavirin. Men receiving ribavirin who are sexually active with women will also have to be willing to commit to abstinence from sexual activity, or use of two forms of contraceptive during treatment and for the 6 months after completion of ribavirin.

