4.3.2 Incarcerated Participants

Participants who become incarcerated during the course of the study may have to be withdrawn; continued collection of data from incarcerated subjects would be on a case-by-case basis after consultation with the IRB.

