6.4 Study procedures – HCV treatment

During HCV treatment and in the follow-up period, patients with HCV will undergo monitoring for treatment adherence and safety per Standard of Care. Laboratory parameters and imaging used as part of the study endpoints are listed below. See Appendix B Study Schedule.

Cholesterol measurements

Patients' total cholesterol and LDL cholesterol will be obtained at screening and week 72 for cardiac risk calculations.

Cardiac biomarker and systemic inflammation assessment

For all participants, labs will be drawn at screening, week 24, and week 72: high sensitivity CRP (hSCRP), high sensitivity TRP (hsTRP), soluble markers of inflammation (IFN- γ , TNF- α , IL-6, CXCL9, CXCL10, CXCL11) and activated and exhausted naïve and memory T cells (percent of CD8+ and CD4+ T-cells which are HLA-DR+, CD38+, Tim-3+, or PD-1+).

Cardiac MRI

A subset of patients will undergo cardiac MRI; up to 12 patients will be recruited from each of the three groups to undergo cardiac MRI at the NIH clinical center at Day -7 (interim visit) and week 72. Patients who are claustrophobic or cannot tolerate the MRI procedure will not be selected for this portion of the study. Cardiac MRI will be utilized to assess changes in myocardial injury, degree of post-contrast enhancement, T1 mapping, and the function of the myocardium. See Appendix C for more details.

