10.1 Return of Withdrawn/Removed Subjects

A participant who has withdrawn may not return to the study.

11 Remuneration Plan for Subjects

Participants will not be renumerated for receiving HCV treatment.

Participants will receive \$25 remuneration as gift cards at those visits where stored sample blood draws are completed. Those visits are Screening, week 24, and week 72. If additional visits are needed to obtain bloodwork or imaging, this additional visit would also warrant a \$25 remuneration. We will not exceed a maximum of 3 additional visits and will encourage combined visits.

Participants will receive \$100 remuneration as gift cards provided by UMB study staff whilst working as special volunteers at the NIH site when participants have an MRI. These visits are at the time of day -7 (interim visit) and week 72. [name], [name], [name], and [name], are UMB sub investigators who are also special volunteers at NIH and are fully credentialed and able to see research patients at the NIH. They are also authorized to obtain informed consent, provide remuneration to subjects visiting the NIH site, have access to identifiable data, see patients at NIH and participate in manuscript preparation/review.

12 Monitoring

As this is an observational study with intervention limited to laboratory and radiologic data collection, safety issues are not expected. The PI and the study team will conduct regular monitoring of safety and report to the IRB as specified in section 9.

13 Statistical Considerations

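### Section 10 ends follow-up after a PI-requested withdrawal exactly as after a participant's own, so a week-72 hsCRP not yet drawn is lost even when the participant has not refused it

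*Combined protocol and SAP*

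**What the plan says.** Section 10 (Withdrawal of a Subject) treats two events as one: "Voluntary withdrawal from the protocol may occur at any time at the request of either the participant or the PI". After either request, "all further planned study procedures will be immediately cancelled and further follow-up will be terminated". What has been gathered up to that point is kept: "Samples and data already collected may continue to be used". Section 10 also requires withdrawal on pregnancy. Section 10.1, whose heading covers both withdrawn and removed subjects, adds: "A participant who has withdrawn may not return to the study".

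Three other provisions allow some later contact:
- Section 6.5: "Participants who discontinue HCV treatment prior to treatment completion for medical or personal reasons will be given the option of being followed" on the study schedule for laboratory monitoring.
- Section 4.3.2: for incarceration, "continued collection of data from incarcerated subjects would be on a case-by-case basis after consultation with the IRB".
- Section 9.4.1: adverse events are followed to resolution or stability, if necessary after the participant has left the study.

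For hsCRP, Section 6.4 says "labs will be drawn at screening, week 24, and week 72". Section 13.2 analyses the change from baseline to 18 months with a paired t-test within each group and names no method for missing values. Section 13.1 goes from 30 to 28 per group for SVR failure only.

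**The concern.** A participant who withdraws consent must be left alone. A participant whom the PI removes has not necessarily refused anything, yet the text leaves no route to the week-72 draw. Without that value there is no pair, and the participant drops out of the primary analysis if in Group 1 or 2, or out of the secondary comparisons if in Group 3.

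Removal by the PI is a judgement about a particular person, so it may be related to how that person is doing. If it is, the mean change among the remaining pairs is shifted, and nothing in Section 13 would detect or correct this. The loss is partly avoidable, and a sample not drawn at week 72 cannot be recovered later.

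**Working it through.** **1. Does another provision restore the draw?**

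| Provision | Whom it reaches | Week-72 hsCRP for a PI-removed participant? |
|---|---|---|
| 6.5 | People who stop HCV treatment before completing it | No, if removed after treatment ends or in Group 3 (no HCV treatment) |
| 4.3.2 | Incarcerated participants | Only for that reason, case by case |
| 9.4.1 | People with adverse events | No; event follow-up only |
| 10, data already collected | Everyone withdrawn | No; past visits only |

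The only DAA course length in the protocol is in Section 4.2 ("able to tolerate ribavirin-containing regimen for 16 weeks"), and it applies to a subset. For that subset, 72 − 16 = 56 weeks lie after treatment and outside Section 6.5. This is time outside the provision, not an expected number of removals.

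**2. The plan's own power figure.** Inputs from Section 13.1: 30 × 0.95 = 28.5, taken as 28 pairs; SD 0.15 mg/L, read as the SD of the paired differences; alpha 0.05, taken as two-sided because the plan does not say.

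Normal approximation at 90% power: (1.960 + 1.282) × 0.15 / √28 = 0.092 mg/L. With the noncentral t distribution it is 0.095. Both round to the stated 0.1 mg/L. At 80% power the result is 0.082, so the printed 0.8 mg/L looks like a slip for 0.08; nothing here depends on it.

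**3. Power after lost pairs.** Noncentrality = (0.1 / 0.15) × √n, with n − 1 degrees of freedom:

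| Pairs | Noncentrality | Power for 0.1 mg/L |
|---|---|---|
| 28 | 3.53 | 92.5% |
| 27 | 3.46 | 91.5% |
| 26 | 3.40 | 90.4% |
| 25 | 3.33 | 89.2% |

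Up to two lost pairs leave power at or above 90%; the third takes it just below.

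**4. Scale of a possible bias (assumed inputs).** Suppose k of 28 pairs are lost and their mean change differs by d from that of the rest. The complete-pairs mean then differs from the mean of all 28 by k × d / 28. The documents give neither k nor d. Assume k = 1 to 3, and d = 0.15 to 0.30 mg/L (1 to 2 of the plan's SDs) in either direction:
- Smallest: 1 × 0.15 / 28 = 0.005 mg/L.
- Largest: 3 × 0.30 / 28 = 0.032 mg/L.

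For scale, Section 13.1 cites a baseline median of 0.64 mg/L in SVR patients and a pre-treatment mean of 0.97 mg/L in HCV-monoinfected patients:
- Two-fold fall from 0.64 (0.32 mg/L): 1.7% to 10.0%.
- Two-fold fall from 0.97 (0.485 mg/L): 1.1% to 6.6%.

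The shift is zero if removal is unrelated to the change in hsCRP.

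**The case against.** The strongest reply is that the rule forces little loss. Withdrawal at the PI's request is discretionary, and a PI who wants the week-72 draw need not ask for it. HCV treatment is standard of care, and the research procedures are mainly the draws and the MRI, so withdrawing someone largely means deciding to stop those. If the reasons resemble the PI-judged exclusions in Section 4.3, such as inability to attend visits, many of the lost draws could not have been obtained anyway. The missing dropout allowance and missing-data method are wider problems that apply equally to no-shows.

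Much of this stands. It limits how many values the fix could recover and places the point at minor priority. It does not remove the point: Section 10 states a definite rule, the rule makes no distinction for a removed participant who would still give blood, and Section 6.5 shows that the plan already accepts laboratory follow-up after someone leaves the treatment path.

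A reader might also infer more than the text supports:
- **That everyone who stops HCV treatment is lost, or that earlier data are discarded.** Section 6.5 offers laboratory follow-up, and Section 10 keeps what was collected.
- **That safety follow-up ends.** Section 9.4.1 continues it.
- **That the fall in hsCRP will be overstated.** Nothing in the documents fixes the direction; it could equally be understated.
- **That Group 3 losses weaken the primary test.** The primary hypothesis in Section 3.4 concerns Groups 1 and 2 only.

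**Conclusion.** The point holds as a minor, avoidable weakness in the withdrawal rule. PI-requested withdrawal and withdrawal by the participant have the same consequence, and no other section provides the week-72 hsCRP for a willing participant removed after treatment ends or in Group 3.

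No removal rate is given, so the size and direction of any bias are unknown. Even the upper end of the assumed range, 0.032 mg/L, needs three removals in one group, all from the 28 SVR pairs, with a mean difference of two SDs. The power figures rest on 0.15 mg/L being the SD of the differences and on a two-sided test. On that reading the effect on power is slight: 92.5% falls to 90.4% with two lost pairs and 89.2% with three.

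One case is left open. Section 10 makes withdrawal on pregnancy mandatory, and the text does not say whether any later draw could still be offered.

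**What to change.** In Section 10:
- Limit the end of follow-up to participants who withdraw consent.
- For PI-initiated removal, stop only the procedures that the reason for removal rules out, and offer the remaining scheduled week-24 and week-72 draws in all three groups, on the model of Section 6.5.
- Say explicitly whether the offer covers pregnancy withdrawals. If it does, leave out the MRI and gadolinium (Appendix C already excludes pregnant women) and flag any hsCRP value taken during pregnancy.

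Keep the IRB consultation in Section 4.3.2 for incarceration. In Section 10.1, state that the bar on return does not prevent these offered draws.

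The cost is protocol and consent wording, plus at most two already scheduled draws per person: 2 × $25 = $50 in gift cards at the Section 11 rate. With an assumed 1 to 3 removals per group, 3 to 9 people, that is at most $150 to $450, plus assay cost, which is not given. The site must keep contact with a few removed participants, and some will decline or be unable to attend.
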